#### 8.3 Accrual Estimates

MCW is required (per MCW sIRB) to activate prior to other sites, whose activation times will vary due to internal activation timelines. Accrual is expected at one subjects/month during year 1, and two subjects/month afterwards. Therefore, enrollment is expected to last 29 months; last subject, last dose and assessment are expected to take another 11 months. Therefore, total trial duration would be approximately 40 months.

The study will reach study completion in approximately 10 years (five years for completion of treatment for all patients, and five years of long-term survival follow-up) from the time the study opens to accrual.

# 9 OPERATIONAL CONSIDERATIONS, MULTISITE ADMINISTRATION, SOURCE DOCUMENTS, AND DATA MANAGEMENT

#### 9.1 Staff Training, Changes, and Delegation of Authority Log

Documentation of training completion for required items of training (i.e., training log, CITI completion certification, etc.) and the delegation of authority (DOA) or local context form (as appropriate) must be maintained at each site for all study staff members, uploaded into the shared site study folder, and sent to the MCW Multisite Team upon request.

All site study staff must be adequately trained to perform the delegated task(s) approved by the participating site PI, as recorded in the delegation of authority log, or local context form (as appropriate), and training log (or online training log).

Inform the MCW Multisite Team (via the MCW Multisite Team email) immediately if a change in PI is planned.

#### 9.2 Monitoring Plan

The MCWCC DSMC is responsible for monitoring data quality and subject safety for all MCWCC investigator-initiated clinical trials, according to the approved MCW DSMP.

Unless otherwise specified in the contract/budget, the following monitoring plan will occur under the direction of the MCW Multisite Team:

- Onsite monitoring or remote monitoring within two to four weeks of the first subject enrollment (if applicable, as determined by the MCW Multisite Team).
- Onsite monitoring or remote monitoring (if applicable, as determined by the MCW Multisite Team) visits and outstanding data reports approximately every three months until the MCW PI and DSMC approve that routine monitoring is no longer required.

Short Title: MCW EMBRACE TRIAL 67 Version No.: 3
Version Date: 12/29/2022

- Consents, source documents supporting eligibility, primary and secondary objectives, drug accountability/temperature/shipping/receiving logs (if applicable), and key data points should be provided to the MCW Multisite Team. The monitor may verify certain data points at his/her discretion.
- Data lock at time of interim analysis.
- Study updates via a videoconference meeting may occur (depending upon accrual rate and complexity of trial, at the discretion of the MCW Multisite Team and MCW PI).

#### 9.3 Audit Plan

Audit plans are determined by the DSMP according to risk category:

- Approximately 30% of enrolled subjects per site randomly selected for review (a maximum of 10 subjects per site at each review).
- Consent, eligibility, and objective-based data are reviewed for all files selected.
- One subject file per site (of the 30% mentioned above) randomly selected for a comprehensive review at each time point.
- 100% of regulatory documents.
- The auditor reserves the right to select other subject(s) if deemed necessary (i.e., in case of a significant or repetitive finding).
- An audit occurs every year until the DSMC determines that future audits may be deferred.

Audits may be performed by either the MCW QA department, a contracted business partner, and/or another entity specified in the consent, contract, or budget. Directed audits, outside of those regularly scheduled, may be requested at any time by the MCW Multisite Team or applicable regulatory agency. Studies are subject to random or for-cause audits from the sIRB.

Participating sites must promptly inform the MCW Multisite Team (via the MCW Multisite Team email) of any other external or internal audit/review of this trial prior to its occurrence and send the final findings/report with any corrective action plan to the MCW Multisite Team (via the MCW Multisite Team email).

#### 9.4 Audit and Monitoring Report and Corrective Action Plan (CAP)

Audit or monitoring reports occur in the following manner:

- Sites follow local SOP/practices and communicate with MCW as appropriate.
- Sent to the participating site PI after the date of the audit or monitoring visit.
- Must be shared with any other required entity, as required per local SOPs and policies (e.g., DSMC, sIRB, etc.).
- Include a brief description of findings.
- Address whether a corrective action plan (CAP) is required, and when it is required.
- Indicate if another short-term audit or monitoring visit is necessary, and within what time frame it should occur.

#### 9.5 Deidentified Source Documents, Remote Access to Records, and Shadow Charts

Regulatory authorities, the sIRB, and/or sponsor may request access to all source documents, data capture records and other study documentation for audit or inspection. Direct access to these documents must be guaranteed by the investigators, who must provide support at all times for these activities.

The following (but not limited to) source documentation should be provided to the MCW Multisite Team (via the online shared study folder and/or email):

- Supporting documents for all eligibility criteria (including consent and documentation of consent process).
- Supporting documents for important data points (e.g., primary or secondary endpoints).
- Source(s) indicating all expedited reported events.
- SAE and AESI supporting source documents (e.g., admission/discharge notes and other applicable procedures) and SAE/AESI email confirmations.
- Pharmacy drug accountability/temperature/shipping/receiving logs (uploaded prior to monitoring visits or as requested (or applicable access to these records via institutional practice, e.g., Vestigo).
- Investigator attribution determination (e.g., AE log signoff, etc.)

If a participating site allows monitors and auditors remote or onsite access to their electronic health record (EMR), staff will adhere to their local SOPs. Shadow charts (e.g., paper or electronic copies of the EMR) are maintained according to local SOPs and policies.

#### 9.6 Transferring Subjects

If a participant decides to transfer from the enrolling site to another new participating site, the following occurs:

- The current enrolling site contacts the MCW Multisite Team (via the MCW Multisite Team email) and new participating site.
- Both site PIs agree to the transfer and follow institutional SOPs.
- All data and queries must be completed before transfer.
- After official transfer, documents have been finalized.
  - All applicable source documents are transferred.
  - o Data capture system access is transferred.
  - o The new participating site PI becomes responsible for the participant.

#### 9.7 Retention of Study Documents

Study documents must be retained according to the following requirements:

- Participating sites must maintain all study records according to FDA and applicable regulatory requirement(s).
- Records are retained for at least two years after the last marketing application approval or two years after formal discontinuation of the clinical development of study drugs or according to applicable regulatory requirement(s), whichever is longest. In either case, sites must inform the MCW PI and MCW Multisite Team (via the MCW Multisite Team email) of any intention to no longer retain study records.
- Record retention may be extended per local institution policy or sponsor request.
- If the participating site PI withdraws from the responsibility of keeping the study records, custody must be transferred to a person willing to accept the responsibility.
- The MCW Multisite Team must be notified in an email (via the MCW Multisite Team email) if a custodial change might occur, and approval must be obtained prior to the change.

#### 9.8 Publication and Data Sharing Policy

Publication and data sharing requirements are detailed in the clinical trial agreement. The MCW study PI determines authorship in a multifaceted manner, based on substantial intellectual input, effort, and participation:

Authorship guidelines are as follows:

- First author requirements:
  - o MCW study PI/Co-PI.
  - o Writes the primary manuscript.
- Participating site PI authorship:
  - o Each participating site investigator with at least one enrollment may be eligible for
  - Order determined by top accruing sites.
- Last author:
  - Most senior position who contributed to the protocol development (unless otherwise specified).
- Acknowledgements:
  - o The MCW study PI may include other staff or colleagues, as applicable.
  - o Sponsorship from the drug manufacturer(s) per the drug manufacturer(s)'s contractual requirements.
- Journal or publication author number limitations:
  - o Authors will be removed in reverse order of original order, as determined by the MCW study PI.

#### 9.9 Electronic Data Capture and Timely Data Entry

Participating sites enter electronic data into OnCore®, under the supervision and responsibility of the site investigator. Study-specific case report forms (CRFs) will document outcomes. All study data will be entered into OnCore® via standardized CRFs, in accordance with the study calendar, using single data entry with a secure access account. Designated study staff will complete the CRFs as soon as possible upon completion of the study visit; the investigator will review and approve the completed CRFs. The information collected on CRFs shall be identical to that appearing in original source documents.

Timely data entry is defined as follows (unless otherwise specified in the contract/budget):

- OnCore® entry must occur within 24 hours of consent, enrollment, and withdrawal (for any reason).
- Protocol visit time point data should be entered within four weeks of visit occurrence, unless otherwise requested by the MCW Multisite Team (e.g., prior to DSMC reviews, audit, etc.).
- Deviations should be entered within four weeks of discovery, if not requiring expedited reporting (refer to Section 6).
- Refer to Section 6 for timely reporting of events requiring expedited reporting.

#### 10 REGULATORY COMPLIANCE, ETHICS, AND MANAGEMENT

This study will be conducted in accordance with the ethical principles that have their origin in the Declaration of Helsinki as stated in 21 CFR §312.120(c)(4).

This study will be conducted in compliance with:

• The protocol.

 Federal regulations, as applicable, including: 21 CFR 50 (Protection of Human Subjects/Informed Consent); 21 CFR 56 (Institutional Review Boards) and 45 CFR 46 Subparts A (Common Rule), B (Pregnant Women, Human Fetuses and Neonates), C (Prisoners), and D (Children), and all applicable regulatory requirements. The sIRB must comply with the regulations in 21 CFR §56 and applicable regulatory requirements.

#### 10.1 Activation Letter for Participating Institutions

Study conduct must not occur until an official activation letter has been received at the participating site. After all required institutional and regulatory approvals have been obtained, the MCW PI and MCW Multisite Team issue an activation letter to the participating site. Then, study conduct may begin.

#### 10.2 CAP, CLIA, and Reference Ranges

Participating sites should ensure their laboratory maintains CAP (if applicable) and CLIA certification. The MCW Multisite Team may request reference ranges as necessary.

#### **10.3 Scientific Review Committee**

The MCW Scientific Review Committee (SRC) has the following responsibilities:

- Establishing and maintaining a review committee of sufficient size and breadth of expertise to conduct a critical and fair scientific review of institutional cancer-related research involving human subjects.
- Conducting a thorough scientific review of all non-peer-reviewed, cancer-related clinical protocols using a standard format based on specific, predetermined review criteria.
- Assisting MCWCC investigators in the development of scientifically and clinically sound research through well-written protocols.
- Considering protocol feasibility with regard to budget, resources, and competing trials.
- Establishing clear criteria for determining whether ongoing clinical trials are making sufficient scientific progress, including the attainment of adequate subject accrual rates.
- Monitoring all cancer-related research protocols based on the criteria established by the SRC and terminating protocols that do not meet these expectations.
- Ensures that clinical trials are scientifically sound and that approved trials maintain subject accrual goals and scientific progress.

The levels of reviews are full, expedited, or exempt (based on the chair's discretion). Amendments may require SRC review or be exempt from review depending on whether the changes are major or administrative. The SRC may approve, approve with modifications, defer, or disapprove a trial. Furthermore, the SRC identifies low-accruing studies and either warns the disease-oriented team (DOT) chair and MCW PI of low accrual or recommends study closure.

Participating sites will adhere to their local policies regarding scientific review committee approvals.

#### 10.4 Data and Safety Monitoring Committee

The MCW PI only reports DSMC letters to all other participating sites if they meet the FDA definition of requiring reporting (i.e., unanticipated problem), are required to be reported to other sites by the DSMC, and/or result in a significant finding/recommendation/action (e.g., change in study conduct, study closure, study hold). However, all DSMC reports can be sent to participating sites upon request.

After DSMC review of a participating site event, the MCW PI reports the DSMC letter to the participating site where the pertinent event occurred. The most recently approved MCW Data and Safety Monitoring Plan (DSMP) documents must be followed by all participating sites.

The MCW Data and Safety Monitoring Committee (DSMC) has the following responsibilities:

- Reviews the clinical trials for data integrity and safety.
- Reviews all unexpected grade 3, and all grade 4, and 5 adverse events, as well as any others requiring expedited reporting as defined in this protocol.
  - o Non-hematological grade 4 and all grade 5 events must be reported to the DSMC within five calendar days of MCW study staff's knowledge. Hematological grade 4 events can be routine reported.
- Reviews all DSM reports.
- Submits a summary of any recommendations related to study conduct.
- Terminates the study if deemed unsafe for subjects.
- Informs the MCW Multisite Team (via the MCW Multisite Team email) of finalized reports/letters to be sent to the participating sites.

The DSMC will review reports no less than biannually (unless otherwise specified/approved by the DSMC). MCW institutional monitoring of multisite trials will be conducted according to the approved data and safety monitoring plan (DSMP), under the responsibility of the associate director for clinical research (ADCR).

#### 10.5 Subject Confidentiality and Access to Source Documents/Data

Participant confidentiality and privacy are strictly held in trust by the participating investigators, their staff, and the sponsor(s) and their interventions. This confidentiality is extended to cover testing of biological samples and genetic tests, in addition to the clinical information relating to participants. Therefore, the study protocol, documentation, data, and all other information generated will be held in strict confidence.

The study monitor, other authorized representatives of the sponsor, representatives of the Institutional Review Board (sIRB), regulatory agencies or pharmaceutical company supplying study product may inspect all documents and records required to be maintained by the investigator, including but not limited to, medical records (office, clinic, or hospital) and pharmacy records for the participants in this study. The clinical study site will permit access to such records.

The study participant's contact information will be securely stored at each clinical site for internal use during the study. At the end of the study, all records will continue to be kept in a secure location for as long a period as dictated by the reviewing sIRB, institutional policies, or sponsor requirements.

Study participant research data, which are for purposes of statistical analysis and scientific reporting, will be transmitted to and stored in OnCore®. This will not include the participant's contact or identifying information from participating sites outside MCW. Rather, individual participants and their research data will be identified by a unique study identification number. The study data entry and study management

systems used by clinical sites and by MCW research staff will be secured and password protected. At the end of the study, all study databases will be archived at the Medical College of Wisconsin.

## 10.6 Protection from Unnecessary Harm

Each clinical site is responsible for protecting all subjects involved in human experimentation. This is accomplished through the sIRB mechanism and the informed consent process. The sIRB reviews all proposed studies involving human experimentation and ensures that the subject's rights and welfare are protected and that the potential benefits and/or the importance of the knowledge to be gained outweigh the risks to the individual. The sIRB also reviews the informed consent document associated with each study in order to ensure that the consent document accurately and clearly communicates the nature of the research to be done and its associated risks and benefits.

#### 10.7 Changes in the Protocol, Consent, or other Trial Document

A participating site may request changes to trial documents in the following manner:

- Major site-specific changes to the consent and ancillary documents are highly discouraged, though some changes are necessary (e.g., accrual goal updates, local context changes, etc.).
- Any change must be clearly indicated, then submitted to the MCW Multisite Team (via the MCW Multisite Team email) for approval by the MCW PI, the drug manufacturer(s) (if required), and sIRB, prior to implementation.
- MCW PI and sIRB approval must occur prior to implementation of any change, unless all of the following obtains:
  - o Approval cannot be obtained in a reasonable time frame for subject safety and must be implemented immediately for subject safety.
  - The MCW PI, Multisite Team (via the MCW Multisite Team email), and applicable agencies (SRC, DSMC, sIRB as applicable) are informed as soon as possible, if they cannot be informed before implementation.
  - The investigator must then notify the sIRB in writing within five working days after implementation.

The sIRB may provide, if applicable regulatory authority(ies) permit, expedited review, and approval/favorable opinion for minor change(s) in ongoing studies that have the approval /favorable opinion of the IRB. The investigator will submit all protocol modifications to the drug manufacturer(s) and the regulatory authority(ies) in accordance with the governing regulations. Changes to the protocol may require approval from the drug manufacturers.

# APPENDIX 1. PERFORMANCE STATUS CRITERIA

ECOG	Performance Status Scale	Karnofsk	y Performance Scale
Grade	Descriptions	Percent	Description
0	Normal activity Fully active, able to carry on all pre-	100	Normal, no complaints, no evidence of disease
	disease performance without restriction	90	Able to carry on normal activity; minor signs or symptoms of disease
1	Symptoms, but ambulatory Restricted in physically strenuous activity, but ambulatory and able to	80	Normal activity with effort; some signs or symptoms of disease
	carry out work of a light or sedentary nature (e.g., light housework, office work)	70	Cares for self, unable to carry on normal activity or to do active work
2	In bed < 50% of the time Ambulatory and capable of all self-	60	Requires occasional assistance, but is able to care for most of his/her needs
	care, but unable to carry out any work activities Up and about more than 50% of waking hours	50	Requires considerable assistance and frequent medical care
3	In bed > 50% of the time	40	Disabled, requires special care and assistance
	Capable of only limited self-care, confined to bed or chair more than 50% of waking hours	30	Severely disabled, hospitalization indicated Death not imminent
4	100% bedridden	20	Very sick, hospitalization indicated Death not imminent
	Completely disabled Cannot carry on any self-care Totally confined to bed or chair	10	Moribund, fatal processes progressing rapidly
5	Dead	0	Dead

Short Title: MCW EMBRACE TRIAL 74 Version No.: 3
Version Date: 12/29/2022

# APPENDIX 2. SUBJECT LOST TO FOLLOW-UP LETTER

Date:	
Dear,	
The research study team has been unable to contact you reg II Study of Maintenance Belantamab Mafodotin (Blenrej Receptor-T Cell Therapy in Patients with Relapsed and/or la participated in.	o®) after BCMA-directed Chimeric Antigen
We would like to discuss how you are doing and if we may	continue contacting you.
Please contact us at	
Sincerely,	

Short Title: MCW EMBRACE TRIAL Version No.: 3 75

Version Date: 12/29/2022

# APPENDIX 3. IMWG MULTIPLE MYELOMA RESPONSE CRITERIA

(Based on Kumar et al., 2016)

Stringent complete response (sCR)	Complete response (defined below) AND normal free light chain (FLC) ratio and absence of clonal cells in marrow by IHC.
Complete response (CR)	Negative immunofixation (serum and urine) AND disappearance of any plasmacytomas AND <5% plasma cells in marrow by IHC.
Very good partial response (VGPR)	Serum and urine M-protein detectable by immunofixation but not by electrophoresis; greater than or equal to 90% reduction in serum M-protein level AND urine M-protein level less than 100 mg per 24 hr.
Partial response (PR)	50% or greater reduction of serum M-protein AND reduction in 24 hr urinary M-protein by 90% or greater or to less than 200 mg/24 hr; if serum and urine M-protein are unmeasurable, must have a 50% or greater reduction in the difference between involved and uninvolved FLC level; if M-proteins and FLC assays are non-contributory, a 50% or greater reduction in plasma cells is required.
Minimal response	Reduction in serum-protein by 25 to 49% AND reduction in urine M-protein by 50 to 89%.
Stable disease (SD)	Not meeting any of the definitions listed in this table for response or PD.
Progressive disease (PD)	Increase of 25% from lowest confirmed response value (one or more of the following): Serum M-protein (absolute increase must be  0.5 g/dL); Serum M-protein increase  1 g/dL, if the lowest M component was  5 g/dL; Urine M-protein (absolute increase must be  200 mg/24 hr.); appearance of a new lesion.

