#### 2.2 Primary Endpoint

1. Twelve-month conditional progression-free survival (PFS), defined as the probability of being alive without progression/relapse or death at 12 months from the time of CAR-T administration conditional on being alive without progression/relapse at 3 months from the time of CAR-T. Follow-up time will be counted from the date of CAR-T cell infusion, left-truncated at the start of study treatment, to the date of first documentation of progression or death due to any cause. Patients last known to be alive and progression-free are censored at date of last contact.

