#### **Inclusion Criteria**

Each subject must meet all the following inclusion criteria to be enrolled in the studv:

- 1. Diagnosis of multiple myeloma with measurable disease (at the time of diagnosis: serum M-protein ≥ 0.5 g/dL or urine M-protein ≥200 mg/24 hour or involved serum-free light chain >10 mg/dL provided that the ratio of involved/uninvolved light chain is abnormal). Patients with no biochemically measurable disease may be enrolled if bidirectionally measurable plasmacytomas or bone marrow plasmacytomas >10% are present prior to CAR-T infusion (sites must explicitly identify these patients to the MCW Multisite Team upon enrollment, as only four of these patients will be permitted on study, after which no future patients will be permitted to be enrolled).
- Received at least four prior lines of therapy (including a PI, IMiD, and anti-CD38 monoclonal antibody – note radiation therapy is considered a line of therapy) given before anti-BCMA CAR-T cell therapy, and has not progressed/relapsed after receiving CAR-T therapy.
- Achieved at least SD to CAR-T therapy and remained progression-free after anti-BCMA CAR-T administration until enrollment (this requirement is also necessary prior administration of first study drug).
- Voluntary consent (per sIRB requirements) must be given before performance of any study-related procedure not part of standard medical care, with the understanding that consent may be withdrawn by the subject at any time without prejudice to future medical care.
- 5. Age  $\geq$  18 years.
- Life expectancy  $\geq$  six months.
- 7. Eastern Cooperative Oncology Group (ECOG) performance status 0–2.
- 8. Creatinine clearance (CrCl)  $\geq 30 \text{ mL/min/1.73 m}^2$  (using formula MDRD).
- Adequate hepatic function evidenced by AST and ALT  $\leq$  2.5 x ULN, bilirubin  $\leq$ 9. 1.5 x ULN (isolated bilirubin ≥1.5xULN is acceptable if bilirubin is fractionated and direct bilirubin <35%).
- 10. Adequate bone marrow function evidenced by hemoglobin  $\geq 8$  g/dL, platelets ≥75,000/mm³ (without transfusion of platelets in the prior seven days) and absolute neutrophil count ≥1,500/mm³ (growth factors are allowed during screening, but not within seven days prior to obtaining this result).
- 11. Spot urine (albumin/creatinine ratio) < 500 mg/g (56 mg/mmol) OR urine dipstick negative/trace (if  $\geq$  1+ only eligible if confirmed  $\leq$  500 mg/g (56 mg/mmol) by albumin/creatinine ratio (spot urine from first void).

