#### 8.2 Determination of Sample Size and Accrual Rate

#### 8.2.1 Primary Endpoint

The primary endpoint of the study is the 12-month progression-free survival (PFS) with time counted from the CAR-T infusion conditional on being alive and progression-free at day +90 post CAR-T. An event will be defined as documented progression or death for any cause, subjects without an event will be censored at the last date known to be alive without progression. Left truncation at the time of the start of study treatment will be used to adjust for "immortal time" after day +90 before study enrollment.

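### Appendix 3 has no progression rule for serum free light chains, marrow plasma cells or growth of an existing plasmacytoma, so relapses seen only there can be missed or scored inconsistently in the primary PFS

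*Combined protocol and SAP*

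**What the plan says.** The primary endpoint is 12-month PFS conditional on being progression-free at day 90, compared with a fixed 54%. Section 8.2.1 states: "An event will be defined as documented progression or death for any cause". Section 2.2 adds: "Patients last known to be alive and progression-free are censored at date of last contact".

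Progression is defined only in Appendix 3. The PD row begins "Increase of 25% from lowest confirmed response value (one or more of the following". It covers serum M-protein (with absolute minimum rises), urine M-protein (likewise) and a new lesion, and stops there. The stable-disease row takes whatever remains: "Not meeting any of the definitions listed in this table for response or PD".

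The partial-response row of the same table does go beyond M-protein. When serum and urine M-protein are unmeasurable, the patient "must have a 50% or greater reduction in the difference between involved and uninvolved FLC level"; when FLC is also uninformative, the row falls back on plasma cells.

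Inclusion criterion 1 (Section 4.6) accepts measurable disease by involved FLC alone, "provided that the ratio of involved/uninvolved light chain is abnormal", with no limit on numbers. It continues: "Patients with no biochemically measurable disease may be enrolled if bidirectionally measurable plasmacytomas", or marrow involvement, are present before CAR-T. That second group is limited, "as only four of these patients will be permitted on study".

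FLC is drawn every cycle (Section 3.1 and the study calendar). Calendar footnote 13 requires extramedullary target lesions to be measured and followed by the sum of products of diameters (SPD). Neither measurement has a PD threshold.

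**The concern.** The table lets a patient be scored as responding on FLC or plasma cells but gives no route to progression on the same parameter. Because the stable-disease row is tied to the table's own definitions, the literal result for an FLC-only relapse is stable disease.

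That matters most in the primary analysis. A relapse that is not scored leaves the patient event-free at month 12, or censored if follow-up for progression ends before a scorable event. Either way the Kaplan-Meier estimate moves up, and a single-arm comparison with a fixed value has no control arm to absorb the shift. If some sites use the printed table and others use fuller IMWG criteria, the same relapse is scored differently by site.

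PD also decides when treatment stops (Section 5.1) and whether a patient may receive the first dose (exclusion criterion 2), so the gap leaves those decisions to individual judgement as well.

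**Working it through.** **1. Eligibility against the PD row**

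| Route to measurable disease (inclusion 1) | Limit | Used in the PR row | Used in the PD row |
|---|---|---|---|
| Serum M-protein | none | yes | yes |
| Urine M-protein | none | yes | yes |
| Involved FLC with abnormal ratio | none | yes | no |
| Marrow plasma cells | up to 4 in total with the next row | yes | no |
| Existing plasmacytoma | up to 4 in total with the row above | no | no (only a new lesion counts) |

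For all patients, deaths, new lesions and qualifying M-protein rises remain events. Calendar footnote 11 requires urine electrophoresis only when the urine M-spike is the main parameter, so the urine criterion may not be tested in an FLC-only patient.

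**2. The plan's own power figure.** Inputs (Sections 8.2.2 and 8.2.3): n = 45, null 0.54, alternative 0.74, one-sided 5%, stated power 84%. The plan tests a Kaplan-Meier estimate by z-test. A simple stand-in is an exact binomial rule that declares success at 31 or more event-free of 45:

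- P(X ≥ 31 | 0.74) = 83.0%, close to the stated 84%.
- P(X ≥ 31 | 0.54) = 3.05%.

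**3. Effect per affected patient.** Let m be the share of an affected patient's events that go unscored. At a true 54%, that patient's apparent chance of being event-free is 0.54 + 0.46m. With k affected patients the expected estimate is 0.54 + 0.46·m·k/45. For k = 1 and m = 0.5 the shift is 0.23/45 = 0.0051, about 0.5 percentage point. This does not depend on which parameter makes the patient affected.

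**4. Illustrations under the exact rule** (k and m are assumptions)

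| k | m | Apparent PFS when truth is 54% | Type I error |
|---|---|---|---|
| 0 | – | 54.0% | 3.1% |
| 2 | 0.5 | 55.0% | 4.1% |
| 4 | 0.25 | 55.0% | 4.1% |
| 4 | 0.5 | 56.0% | 5.3% |
| 4 | 1 | 58.1% | 8.5% |

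A simulation closer to the planned analysis (20,000 runs, exponential PFS, entry over one month after day 90, left-truncated Kaplan-Meier, log-log z-test, no interim) gives type I error of 4.3% at k = 0 and 6.7% at k = 4, m = 0.5. In that last case the mean estimate is 56.0% if the missed relapses count as progression-free and 55.5% if they are censored at the missed event.

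**5. What is actually measured before month 12.** Treatment starts on day 90–120 and cycles last 56 days. Month 12 is about day 365.

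- FLC: cycle 2 (day 146–176), cycle 3 (202–232), cycle 4 (258–288) and cycle 5 (314–344). That is four draws after the cycle 1 day 1 sample.
- Marrow (footnote 16): cycle 3 day 1, then cycle 7 day 1 (day 426–456). That is one on-treatment marrow.
- Routine lesion imaging after screening: in the calendar's cycle 6 column, nominally day 370–400 or later. The exception is a PET-CT repeated at cycle 3 day 1 if positive at screening (footnote 14).

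For FLC the data exist and only the threshold is missing. For marrow and lesions the scheduled data inside the primary window are also sparse.

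**The case against.** **The table condenses a named standard.** Appendix 3 is headed IMWG, cites a published version as its basis, and the response endpoint is by IMWG criteria. Experienced sites may well apply the fuller rules, and the coordinating centre receives source documents for endpoints (Section 9.5). This stands in part: it makes inconsistent scoring likelier than total omission. It does not close the gap. The stable-disease row points to its own table, the documents do not say which reading governs, and central staff have no written threshold to check against.

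**The illustration fits the wrong group.** A reader might infer that the missing thresholds explain the whole rise to 55.0–58.1% for the four capped patients. The documents do not support that. With one on-treatment marrow and little or no routine lesion imaging before month 12, much of any missed or delayed progression in that group would come from the assessment schedule. This objection stands.

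**The error-rate effect is within modelling noise.** Baseline type I error is 3.1% under the exact rule, 4.3% in the one-stage simulation and 6.1% in a two-stage simulation with the stated futility rule. That 3-point spread exceeds the 2.2 to 2.4 points added by the half-missed case. This also stands, so 8.5% is a ceiling for an extreme assumption and not a forecast.

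**Censoring at a change of therapy is not stated.** This is correct. Section 3.1 ends disease evaluations at a new anti-cancer treatment, and the endpoint sections censor at last contact or the last date known progression-free. Censoring at therapy change is only an inference, which is why both treatments of a missed relapse are shown.

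**Conclusion.** The gap is real and concerns the definition of the primary event. As written, Appendix 3 classes an FLC-only relapse as stable disease, although FLC-only patients may enrol without a cap. The likely consequences are inconsistent scoring between sites and some upward bias in the 12-month conditional PFS.

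The direction is supported; the size is not. The documents give neither the number of FLC-only patients nor the share of their relapses that would go unscored. The usable figure is about 0.5 percentage point per affected patient if half of that patient's events are missed. It also assumes that the historical 54% comes from data in which such relapses were scored as progression, which the documents do not state.

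A reader might go further and conclude that relapses in these patients never count, or that the trial's type I error is materially broken. Neither follows: M-protein rises, new lesions and deaths still count, the IMWG label invites fuller scoring, and only the all-missed case clearly exceeds 5% under the exact rule. This is a correction that should be made, not a flaw that undermines the design.

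**What to change.** Extend the PD row of Appendix 3:

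1. **FLC (main gain).** When serum and urine M-protein are unmeasurable, PD is a rise of at least 25% from the lowest value in involved-minus-uninvolved FLC, with a stated absolute minimum. It can be applied at every cycle with samples already drawn.
2. **Marrow.** When FLC is also unmeasurable, PD is a stated rise in marrow plasma-cell percentage, using the same 25% rule plus an absolute minimum.
3. **Existing plasmacytoma.** PD is a stated growth in SPD from the lowest value.

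Apply items 2 and 3 to marrows and imaging already scheduled or done for suspected progression. Say in the text that they will act mostly on clinically prompted tests, because few scheduled marrow or imaging assessments fall before month 12; the new wording will not remove delay that comes from the schedule.

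Record at screening which parameter governs progression for each patient. Calendar footnote 11 already works this way for urine. State that the extended table governs scoring at all sites.

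The cost is appendix wording, one CRF field and possibly a slightly lower measured PFS. No visits or samples are added.
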